11.5. Exploratory endpoints

Other exploratory endpoints include:

- Area under the concentration time curve (AUC), using the trapezoidal approach, for intraoperative apixaban or rivaroxaban pharmacokinetic (PK) concentration
- Operative time (measured from start of skin incision to completion of chest closure)
- Duration of ICU stay
- Duration of hospital stay
- 30-day hospital re-admissions

Details on methods of analysis for exploratory endpoints will be provided in the SAP.

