Additional Secondary Effectiveness Endpoints:

- 24-hour chest tube drainage (volume);
- Total platelet transfusions during hospitalization (volume and units);
- Total PRBC transfusions during hospitalization (volume and units);
- Total UDPB events (by class);
- All surgical re-exploration for excessive bleeding
- Total fatal perioperative bleeding events

Exploratory Endpoints:

- Area under the concentration time curve (AUC), for intraoperative apixaban or rivaroxaban pharmacokinetic (PK) concentration
- Duration of index operation (minutes);
- Length of ICU stay;
- Length of hospital stay;
- 30-day hospital readmissions.

Primary Safety Endpoint:

- GCP-level assessment of all AEs during the study period

Additional Safety Endpoints:

- 30-day cardiac mortality
- 30-day all-cause mortality;
- Postoperative stroke during index hospitalization
- Postoperative myocardial infarction (MI) during index hospitalization
- Urgent postoperative coronary revascularization during the index hospitalization
- Postoperative venous thromboembolic events (VTE) during index hospitalization
- Serious device-related adverse events

Investigational design:

This study is a prospective, multi-center, double-blind, randomized pivotal trial to evaluate the safety and effectiveness of DrugSorb-ATR to reduce surgical and early post-surgical bleeding in patients undergoing cardiothoracic surgery requiring CPB \leq 36hrs after last dose of apixaban or rivaroxaban. Bleeding will be measured by a ranked composite endpoint of: fatal bleeding occurring within 48hrs of the index operation, moderate, severe, or massive perioperative bleeding events (UDPB \geq 2), and 24-hour chest tube drainage. Subjects will be randomized in a 1:1 ratio to either standard of care (SOC) alone (control arm) or standard of care plus intraoperative apixaban/rivaroxaban removal with DrugSorb-ATR integration in the CPB circuit (investigational arm). In the control arm a sham device that is not actively connected to the CPB circuit will be placed in the identical location as the DrugSorb-ATR cartridge in the investigational arm, with the entire set-up covered by a drape to maintain the blind. Subjects will be followed out to 30 days after the surgical procedure for assessments of adverse events (AE) and survival.

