The fatal bleeding events within the primary effectiveness endpoint are limited to the 48-hour postoperative window to include only those events likely to be modifiable by the intervention. Timing of re-initiation for therapeutic anticoagulation will be at the discretion of the treating physician, based on his/her assessment of continued bleeding risk vs. thrombotic risk (**Section 9.1.3**). Given that there is reasonable likelihood for resumption of anticoagulation as early as postoperative day two, there is high probability that fatal bleeding occurring > 48 hours post-op would be independent of DrugSorb-ATR effectiveness.

The UDPB scale is a standardized bleeding definition that was specifically designed by experts to capture early bleeding after cardiac surgery and is based on the following 9 criteria occurring either in surgery or during the first postoperative day: (1) delayed sternal closure, (2) postoperative chest tube output, (3) packed red blood cell transfusion, (4) fresh frozen plasma transfusion, (5) platelet transfusion, (6) cryoprecipitate transfusion, (7) use of factor concentrates, (8) use of recombinant activated factor VII (rFVIIa), and (9) surgical re-exploration. [35] The UDPB scale defines 5 perioperative bleeding classes (0-4) as shown in **Table 1** (below). Importantly, it has been demonstrated that higher classification within the UDPB is associated with significantly worse immediate and late outcomes, including both in-hospital and 30-day mortality rates. [35] [36]

Table 1. Bleeding Class According to the Universal Definition of Perioperative Bleeding in Adult Cardiac Surgery

Class	Sternal closure delayed	Postoperative chest tube blood loss within 12 h (mL)	PRBC (units)	FFP (units)	PLT (units)	Cryoppt	PCCs	rFVIIa	Reexploration/tamponade
0 (Insignificant)	No	< 600	0*	0	0	No	No	No	No
1 (Mild)	No	601-800	1	0	0	No	No	No	No
2 (Moderate)	No	801-1000	2-4	2-4	Yes	Yes	Yes	No	No
3 (Severe)	Yes	1001-2000	5-10	5-10	N/A	N/A	N/A	No	Yes
4 (Massive)	N/A	>2000	>10	>10	N/A	N/A	N/A	Yes	N/A

PRBC = packed red blood cells; FFP = fresh frozen plasma; PLT = platelet concentrates; Cryoppt = Cryoprecipitate; PCCs = prothrombin complex concentrates; rFVIIa = recombinant activated factor VIIa; N/A, not applicable

For purposes of UDPB, PRBC, PLT, FFP, and Cryoppt transfusions are counted beginning at **chest closure**. PCC and rFVIIa transfusions are counted beginning at the start of the procedure.

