6.1. Pre-randomization Stratification

Pre-randomization stratification will be performed on three levels, based on the rationale described below:

1. By preoperative DOAC type (either apixaban or rivaroxaban), to control for unanticipated differences between component drugs
2. By study site, to control for differences in institutional protocols for bleeding and transfusion management. Institutions may also differ in metrics utilized for clinical decision-making (e.g., decision to delay sternal closure, or surgical reoperation).
3. By the intended surgical procedure, to control for differing procedure-specific bleeding risks, and duration of CPB (i.e., device exposure) as detailed below:
 - CABG alone (irrespective of number of grafts); or
 - All other cardiothoracic procedures including but not limited to combination procedures (i.e., CABG + aortic/mitral valve procedures, double heart valve procedures, etc.), aortic interventions, and combination aortic + cardiac interventions. These surgeries generally require longer CPB time than CABG alone.

Of note, during the pre-procedure and intraoperative periods, the intended procedure may change due to factors that could not be adequately anticipated in advance of the procedures. These day-of-surgery changes to the planned operations may result in the completion of a procedure that a) does not align with eligibility criteria, or b) alters stratification. Any change to the intended procedure occurring on the day of surgery that is not updated in the final IxRS assignment will be considered a protocol deviation. These protocol deviations will be noted in a deviation log for data analysis considerations at the conclusion of the trial. All subjects who have any of the above changes to their intended procedures should progress through the study as per the protocol.

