9.1. Procedures and Assessments by Study Phase

Subjects are considered enrolled in the study at the time which consent or assent (in the case of a proxy providing permission for an incapacitated subject) to participate in the study is provided. Details on the consent process are provided in [Section 15.3](#) and the ethics of consenting non-vulnerable and vulnerable (incapacitated) populations are detailed in [Appendix 3](#).

[figure not shown]
Subjects who do not meet study entry (inclusion/exclusion) criteria are screening failures and will exit the study. Treated subjects will be followed up through 30 days after the surgical procedure.

The start of the investigation is defined as the date of consent to enroll the first prospective subject. The end of the investigation is defined as the date of the last subject's last contact or assessment (whether scheduled or unscheduled).

The investigation is divided operationally into 6 phases:

- Screening Phase – the period between the time consent/assent is provided for study participation and the start of the surgical procedure with CPB
- Pre-CPB Phase – the period within 2 hours before start of the operation with CPB (time of skin incision). *Note: The Pre-CPB Phase may overlap with the Screening phase.*
- Operation Phase – the start of the surgical procedure (defined as skin incision) until chest closure.
- Post-CPB Phase – the period from the end of CPB up to admission to the Intensive Care Unit (ICU). *Blood sampling for drug removal obtained in the post-CPB phase should be drawn as soon as possible following the end of CPB, and no later than 30min after the subject has been disconnected from the CPB circuit.*
- Post-operation Phase – from admission to the ICU through Day 29 or the point of discharge from hospitalization, whichever is sooner. **Discharge from hospitalization** means the date of initial discharge from the hospital in which the cardiothoracic surgery was completed (i.e., index procedure) irrespective of discharge to home care, secondary care or other rehabilitation unit.
- Day 30 Evaluation Post-Cardiothoracic Surgery – The subject status on postoperative day 30 will be evaluated by telephone contact, in-person follow-up visit, or review of medical records. Assessment of mortality (i.e., vitals status), blood product transfusions, and other adverse events will be performed.

An overview of the investigation design is shown in [Figure 5](#).

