11. STATISTICAL CONSIDERATIONS

General statistical considerations: descriptive summaries will be presented using mean with standard deviation (SD), median, minimum and maximum for continuous variables and as count and percent of subjects for categorical variables. Inferential statistical tests will be two-sided and use alpha (α) of 0.05 as a critical value, unless noted otherwise. Statistical analysis will be carried out using SAS Version 9.4 or later and/or R software language.

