^f In all females of childbearing potential. Performed in serum. Pre-consent test results done during the current admission MAY be used. Pre-consent test results done before the current admission MAY NOT be used.

^g Refer to [Appendix 2](#) for a list of evaluations in the hematology, clinical chemistry, cardiac biomarker, and coagulation tests. During Screening, if consented subjects enter the Operation Phase without post-consent evaluation of hematology, clinical chemistry, or coagulation tests to record, the last pre-consent laboratory values MAY be used. Intraoperative ACT is documented in the ACT log, and not recorded in the Coagulation Test eCRF.

^h Vital signs include supine blood pressure, pulse rate, respiratory rate, oxygen saturation, and body temperature.

ⁱ Duration of CPB = time from the start of CPB to end of CPB, which may differ from duration of operation. Flow rate and flow duration for the device will be recorded q30±5min while patient is on CPB; flow rates are not mandated while subject is on hypothermic circulatory arrest (HCA).

^j Details regarding the surgical type will be recorded. Delayed sternal closure will be recorded. *Re-exploration/re-thoracotomy will be recorded according to the same schedule as AEs and documented in the re-operation eCRF.*

^k ACT will be obtained once at 30min into CPB ±15min, and once within 30min post-protamine administration (post-CPB)

^l During the operation phase, arterial blood gas analysis will be obtained at the following time periods: within 30min pre-CPB, 30±15min into CPB, within 30min post-CPB, and upon admission to the ICU

- ^m Blood product administration will be monitored and recorded from the point of consent through discharge. Cell Saver will **not** be included as blood product administration. Blood loss and bleeding events will be monitored and recorded through follow-up, and drainage will be monitored from chest closure to 12h post-op (for UDPB class) and continued from 12hr post-op through at least 24h post-operation. Measurement of drainage after 24h and through time of chest/mediastinal drain removal will be per SOC.

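### Operative time runs to completion of chest closure, so for a subject left with an open sternum the literal rule adds the wait until later closure (minor: exploratory endpoint)

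*Combined protocol and SAP*

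**What the plan says.** The synopsis lists the exploratory endpoint as "Duration of index operation (minutes", with no start or stop point. Sections 4.3.4 and 11.5 supply the derivation, in the same words in both places: "Operative time (measured from start of skin incision to completion of chest closure". Section 9.1 bounds the Operation Phase in the same way, from "the start of the surgical procedure (defined as skin incision) until chest closure".

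The protocol also expects that some chests will not be closed at the index operation. Section 3 lists the criteria of the universal bleeding definition, beginning "1) delayed sternal closure, (2) postoperative chest tube output", and Table 1 places a subject with delayed sternal closure in class 3. Section 6.1 gives the "decision to delay sternal closure, or surgical reoperation" as an example of a decision that may differ between institutions. Footnote j of Table 6 states: "Delayed sternal closure will be recorded".

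On analysis, section 11.5 says only that "Details on methods of analysis for exploratory endpoints will be provided in the SAP". The general default in section 11 is to report "mean with standard deviation (SD), median, minimum and maximum for continuous variables". Operative time is not in the testing hierarchy of section 11.3, which ends with pRBC transfusions.

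**The concern.** The derivation and the endpoint's name describe the same quantity only when the chest is closed before the subject leaves the operating room. For a subject who leaves with the sternum open, completion of chest closure is, taken literally, the later closure. The recorded value then includes the time spent waiting with an open chest. No section gives a different stop point for these subjects, and section 9.1 does not help because it ends the Operation Phase at the same event.

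What is at stake is how this one endpoint is interpreted. A very long interval in one or two subjects can dominate an arm's mean and SD. Delayed closure is also itself a bleeding criterion within the primary endpoint. If the device reduces bleeding, such values would tend to fall in the control arm, and operative time would then partly re-count bleeding instead of measuring time in surgery.

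**Working it through.** **Plan's own figure.** There is none to reproduce: the documents state no mean, SD, effect, power or test for operative time. As a check of method on the same trial, a two-sample t-test with 29 per group, a difference of 40 and an SD of 40 gives 96.3% power, as section 11.1 states.

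**Inputs from the documents.** 57 evaluable subjects per arm (section 11.1); two-sided alpha of 0.05 (section 11).

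**Assumptions, not in the documents.** Ordinary operative time 300 min, SD 90; added delay d of 24, 48 or 72 h (1,440, 2,880 or 4,320 min); k delayed closures in an arm of 57; a true difference of 0 or 50 min.

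**Step 1: two records under the literal rule.** Incision 08:00, closed 13:00: 300 min, which is correct. Incision 08:00, out of the operating room with the chest open at 14:00, closed 48 h later: 360 + 2,880 = 3,240 min, against 360 min of operating time.

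**Step 2: mean and SD of one arm.** With p = k/57, mean = 300 + p·d and SD = √(90² + p(1 − p)d²). For k = 1 and d = 1,440, p = 0.01754. The mean is 300 + 25.3 = 325 min and the SD is √(8,100 + 0.01724 × 2,073,600) = √43,841 = 209 min.

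| k | Delay | Mean (min) | SD (min) |
|---|---|---|---|
| 0 | – | 300 | 90 |
| 1 | 24 h | 325 | 209 |
| 1 | 48 h | 351 | 389 |
| 1 | 72 h | 376 | 574 |
| 3 | 24 h | 376 | 334 |
| 3 | 48 h | 452 | 649 |
| 3 | 72 h | 527 | 969 |

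**Step 3: power for a true 50-min difference** (4,000 simulated trials per setting, 57 per arm).

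| Delayed closures | Welch t-test | Mann-Whitney |
|---|---|---|
| None | 83–84% | 81–82% |
| 1 in each arm | 5% (24 h), about 0% (48–72 h) | about 80% |
| 3 in each arm | about 0% | 74–76% |

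If cases instead arise at random, with a treated rate 0.6 times the control rate and delays of 24–48 h, Welch power is about 32–46% at a 2% control rate and 19–32% at 5%. Mann-Whitney power stays at about 80–82%. The t-test loss is smaller here than with one case fixed in each arm because in many trials an arm has no case.

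**Step 4: no true difference.** Three cases in control and none in treatment shift the mean difference by 76, 152 or 227 min (24, 48, 72 h), but the median difference by only about 6 min. For that fixed split the Welch test rejects in 16.9%, 8.4% and 2.8% of trials. With cases at random as in step 3 and delays of 24–72 h, it rejects in about 2–4% at a 2% control rate and 6–7% at 5%.

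**Step 5: would a case occur at all?** At 2% in both arms, 1 − 0.98^114 = 90%. At 2% in control and 1.2% in treatment, 1 − 0.98^57 × 0.988^57 = 84%. Both rates are assumed.

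**The case against.** The strongest reply is that the synopsis speaks of the index operation, in minutes. A later return to close the sternum can be read as lying outside that operation, and Table 6 footnote j already sends re-explorations to a separate eCRF. On that reading no subject is given days of surgery. This stands to the extent that the documents contain no explicit scoring rule for an open chest, so a reader who infers that every such subject will be scored with days goes further than the text. It does not rescue the derivation. The stop point is written out twice and, for these subjects, it does not match the endpoint's name. If sites or programmers may choose between the readings, the endpoint is inconsistent.

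A second reply is that the loss of power depends on a mean-based test that the plan does not name for this endpoint. The default summary includes the median, minimum and maximum, so a value near 3,240 min would be visible. For chest tube drainage and transfusions, section 11.3 moves to a nonparametric test if t-test assumptions fail. This largely stands: under a rank test most of the harm disappears. But that fallback is not stated for operative time, the mean and SD are also reported by default, and a robust test does not turn the wait for closure into operating time.

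A third reply is that the endpoint is exploratory and that delayed closures are recorded, so the SAP can handle them. This stands as to severity. Identifying the subjects does not, however, supply the time at which their index operation ended if that time was never collected.

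**Conclusion.** The stated stop rule mis-scores a group of subjects whom the protocol foresees. Under the assumed 300 ± 90 min and a delay of 24–72 h, one case in 57 raises an arm's SD from 90 to about 209–574 min and its mean by 25–76 min. All of these inputs are assumptions, so the figures are illustrations.

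Two stronger conclusions are tempting. One is that a few delayed closures would swamp the endpoint. That holds only for a mean-based analysis, and none is specified; medians and rank tests change little. The other is that false differences would appear. Mean differences can shift under chance imbalance, but with cases arising at random, spurious significance stayed at about 2–7%; the clear excess (16.9%) needed a fixed split of three against none with a 24 h delay.

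The severity is minor. The endpoint is exploratory, has no alpha and no place in the testing hierarchy, and no primary, key secondary or safety conclusion depends on it.

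**What to change.** In the synopsis, sections 4.3.4 and 11.5, and the SAP:

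- Define operative time as skin incision to the end of the index operation. That end is final closure or, if the chest is left open, application of the temporary covering or departure from the operating room. Choose one of these two and state it.
- Capture that time in the eCRF, and exclude later returns to the operating room.
- Report the number of delayed sternal closures by arm, next to operative time.
- Summarise or compare operative time by the median or a rank-based method.

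The cost is one sentence of text and one extra time field. The field is best added prospectively, because an analysis rule written later cannot recover a time that was not collected. Under the assumptions above, leaving out the delay keeps the SD at 90 min and power for a 50-min difference at about 83–84% (t-test) or 81–82% (Mann-Whitney).

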11.6. Interim Analysis

An interim analysis with unblinded efficacy assessment is planned once 70% of evaluable subjects (n=40 per group) have completed the primary effectiveness assessment, including follow-up period. All data for the interim primary effectiveness endpoint will be fully adjudicated by the CEC prior to analysis. The interim evaluation will be performed with possible early stopping for efficacy on the basis of a Lan-DeMets O'Brian-Fleming spending function, which generates group-sequential boundaries that resemble O'Brian-Fleming boundaries, with experiment-wise error preserved at 0.05. [44, 45] Based on simulation results, a Win Ratio Z-value boundary of 2.44 would need to be crossed, corresponding to a two-sided p-value of 0.0148. Should the interim efficacy boundary not be crossed, a total alpha of 0.0148 would be spent at the interim, plus 0.0352 spent at the final analysis. In this case, at the final analysis a Win Ratio Z-value of 2.00 would need to be crossed, corresponding to a p-value of 0.0456, to declare a statistically significant Win Ratio result favoring the treatment arm. The estimated probability of stopping due to efficacy at the interim is >88.1%.

To maintain study blinding, the interim analysis will be conducted by an independent unblinded statistician separate from the day-to-day operational team with appropriate experience. Enrollment will not be paused during the interim analysis. Interim analysis results will be shared only with the DSMB, which will make a decision to either stop the study early due to overwhelming efficacy or continue until the final analysis. The FDA will be immediately notified of any decision by the DSMB to halt or terminate the study early. Should the study stop early, a final analysis will also take place that will include any additional subjects who were treated and followed-up during the conduct of the interim analysis.

To prevent potential operational bias resulting from the interim analysis, the clinical personnel at sites may not be informed of the interim results. Details on the interim analysis methodology will be provided in the SAP.

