Approximately 120 combined DOAC subjects meeting the study inclusion criteria ([Section 4.4.1](#)) will be randomized in a 1:1 ratio to the treatment and control arms. A combined DOAC population is planned for analysis in the current study since apixaban and rivaroxaban share the same mechanism of action, same indications for use, same risk for post-surgical bleeding outcomes, have been shown in *ex vivo* testing to have nearly identical removal rates when treated with the study device, and are therefore considered exchangeable.

In terms of the composite primary effectiveness bleeding endpoint, while bleeding is known to be of significant risk in patients on both apixaban and rivaroxaban undergoing CT surgery without preoperative washout, literature quantifying postoperative bleeding outcomes is limited in this specific population. However, published real-world use experience from the Asklepios Klinik St. Georg research group (Hamburg, Germany) has demonstrated highly similar treatment effects for intraoperative CytoSorb® removal of ticagrelor and rivaroxaban in patients undergoing emergent CT surgery. [12] The difference between treatment and control groups regarding postoperative blood loss (in the form of 24hr chest tube drainage volume), reoperation rates for bleeding, and transfusion volumes were comparable between the ticagrelor and rivaroxaban cohorts. Thus, for the purpose of this study, we will anticipate the same treatment effects for DrugSorb-ATR therapy in subjects

undergoing CT surgery (within 36 hours of last DOAC dose) as were utilized for the STAR-T trial (which enrolled subjects undergoing CT surgery within 48 hours of last ticagrelor dose). The difference in timing between last drug dose and start of surgery for the DOAC vs. ticagrelor studies is necessary due to the difference in recommended washout periods between the DOACs and ticagrelor.

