Because of exchangeability between apixaban and rivaroxaban, the anticipated proportions of individual DOACs expected in the trial (ranging from 40% - 60%, reflective of real-world use patterns), are not assumed to impact power or sample size. Assuming a 5% dropout rate, a total of 114 subjects (57 per arm) are expected to be evaluable for effectiveness and safety. Sample size is based on published response rates for the primary effectiveness Win Ratio sub-components, as noted for rivaroxaban and ticagrelor (above) with a bridge to apixaban, and can be calculated via an iterative simulation process with programming code available in an appendix to Redfors et al. (2019). [16] As a sensitivity exercise, power was estimated under varying conditions where the ratios of apixaban to rivaroxaban subjects were allowed to range from 40% to 60%, for either drug, and under assumptions of +/-5% worse vs. better outcomes for apixaban as compared to rivaroxaban (see **Table 3**). Power for the study to reject a false null hypothesis is formally estimated where apixaban is assumed equally comparable to rivaroxaban, at a subject ratio of 50:50 (see **bold** results in **Table 3**, below).

Table 3. Win Ratio Effect Size Assumptions with Power and Sample Size Estimates Under Varying Conditions

A:R* Com- para- bility	Ratio A:R	n Per Group	Effect Size						Power	
			Component #1		Component #2		Component #3			
			Fatal Bleeding	UDPB (Class ≥2)	Treatment Event	Control Event	Treatment Event	Control Event		
A Has 5% Higher Event Rate Than R Among Treated Subjects	40:60	Interim Analysis N=39	3.06%	3.00%	24.79%	40.50%	489.6 (253)	800 (253)	88.1%	
	40:60	End of study N=56	3.06%	3.00%	24.79%	40.50%	489.6 (253)	800 (253)	99.3%	
	50:50	Interim Analysis N=39	3.07%	3.00%	24.91%	40.50%	492.0 (253)	800 (253)	87.1%	
	50:50	End of study N=56	3.07%	3.00%	24.91%	40.50%	492.0 (253)	800 (253)	99.2%	
	60:40	Interim Analysis N=39	3.09%	3.00%	25.03%	40.50%	494.4 (253)	800 (253)	86.0%	
	60:40	End of study N=56	3.09%	3.00%	25.03%	40.50%	494.4 (253)	800 (253)	99.2%	
A = R Event Rate Among Treated Subjects	40:60	Interim Analysis N=39	3.00%	3.00%	24.30%	40.50%	480 (253)	800 (253)	91.3%	
	40:60	End of study N=56	3.00%	3.00%	24.30%	40.50%	480 (253)	800 (253)	99.5%	
	50:50	Interim Analysis N=39	3.00%	3.00%	24.30%	40.50%	480 (253)	800 (253)	91.3%	
	50:50	End of study N=56	3.00%	3.00%	24.30%	40.50%	480 (253)	800 (253)	99.5%	
	60:40	Interim Analysis N=39	3.00%	3.00%	24.30%	40.50%	480 (253)	800 (253)	91.3%	

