Using a Finkelstein – Schoenfeld test, a total of 57 subjects per arm ensures power of >99.2% for the primary effectiveness endpoint at the final analysis, using a two-sided alpha (α) of 0.05, and assuming an interim analysis for efficacy at 70% completion. [15] Power for each of the key secondary endpoints is estimated at 96.3% assuming a $40\% \pm 40\%$ mean difference between treatment and control, where N=29 subjects receiving apixaban with N=29 corresponding controls along with parallel numbers of subjects receive rivaroxaban and corresponding control, based on a two-sample t-test assuming equal variance and a two-sided alpha of 0.05. For the 24-hour CTD secondary endpoint, assuming a treatment arm volume of 480 ± 253 mL and control arm volume of 800 ± 253 mL [12] [a discount is applied (see **Table 3** for details) to bring the Active arm up to ~40% reduction on the Control arm], power is similarly estimated at >99.9%. Power for comparisons of platelet transfusions between the treatment arm (0.32 ± 0.9 units) and control arm (1.6 ± 2.2 units) [43] is estimated at 98.0%, based on a two-sample t-test assuming unequal variance and a two-sided alpha of 0.05. Similarly, power for PRBC transfusions between the treatment arm (1.3 ± 2.1 units) and control arm (4.4 ± 5.7) [43] is estimated at 96.7%. Sample size and power for all secondary endpoints were calculated using PASS 2021 (NCSS, LLC. Kaysville, UT, USA, ncss.com/software/pass).

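### The >88.1% interim stopping probability in Section 11.6 names no scenario and matches only one sensitivity row of Table 3, which is run at 39/56 rather than the planned 40/57 per group and contains one inconsistent mean

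*Combined protocol and SAP*

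**What the plan says.** Section 11.6 places the unblinded efficacy look "once 70% of evaluable subjects (n=40 per group") and closes its account of the boundaries with "The estimated probability of stopping due to efficacy at the interim is >88.1" per cent. No scenario is attached to that figure.

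Section 11.1 states that "a total of 57 subjects per arm ensures power of >99.2" per cent at the final analysis, "using a two-sided alpha (α) of 0.05, and assuming an interim analysis for efficacy at 70% completion". The Synopsis (Sample Size) repeats this. Section 11.1 also says which scenario carries the formal estimate: apixaban equal to rivaroxaban at a 50:50 mix. The other rows of Table 3 are described as a sensitivity exercise. They vary the mix from 40:60 to 60:40 and make apixaban 5% worse or better among treated subjects.

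Every interim row of Table 3 is labelled "Interim Analysis N=39", and every end-of-study row is run at 56 per group.

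**The concern.** Section 11.1 says the sample size was chosen to give adequate power at the interim as well as at the final analysis, so interim power is a declared property of the design. Section 11.6 is where a reader looks for the chance of an early stop, and an early stop leaves about 40 per group, plus any overrun subjects, for the secondary endpoints.

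The figure given there cannot be traced to a labelled scenario. If it is meant as a floor over the scenarios, two rows of the source table contradict it. If it is meant as the base case, it comes from the wrong row. The source table was also run for one subject fewer per group than the text plans, at both looks, with no explanation, and one of its inputs does not fit the pattern of the others.

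**Working it through.** **1. Boundaries (Section 11.6).** The plan gives "a Win Ratio Z-value boundary of 2.44 would need to be crossed, corresponding to a two-sided p-value of 0.0148", and "at the final analysis a Win Ratio Z-value of 2.00 would need to be crossed". With Lan-DeMets O'Brien-Fleming spending, 0.025 per side, the alpha spent per side at information fraction t is 2[1 − Φ(z₀.₀₁₂₅/√t)]. At t = 0.70 this gives 0.0148 two-sided, Z = 2.438 at the interim, and Z = 2.000 (p = 0.0455) at the final. Both boundaries reproduce. Using 40/57 or 39/56 as the exact fraction moves the interim value only to 2.434 or 2.445.

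**2. Group sizes.** 120 × 0.95 = 114, which is 57 per arm. 0.70 × 57 = 39.9, so 40. Table 3's pair fits a different total: 0.70 × 56 = 39.2, so 39. Each pair is consistent within itself, but they belong to different evaluable samples.

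**3. Table 3 inputs.** The rows follow base × [apixaban share × (1 ± 0.05) + rivaroxaban share], a rule inferred from the table. For treated 24-hour chest tube drainage, base 480 mL:

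| Scenario | Mix A:R | Rule (mL) | Printed (mL) |
|---|---|---|---|
| A 5% worse | 40:60 | 480 × 1.02 = 489.6 | 489.6 |
| A 5% worse | 50:50 | 480 × 1.025 = 492.0 | 492.0 |
| A 5% worse | 60:40 | 480 × 1.03 = 494.4 | 494.4 |
| A 5% better | 40:60 | 480 × 0.98 = 470.4 | 470.4 |
| A 5% better | 50:50 | 480 × 0.975 = 468.0 | 468.0 |
| A 5% better | 60:40 | 480 × 0.97 = 465.6 | **456.6** |

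The same last scenario's event rates do follow the rule: 3.00 × 0.97 = 2.91% and 24.30 × 0.97 = 23.57%. A digit transposition is the likely cause. The page does not show whether 456.6 was also the value simulated.

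**4. Power.** Allocation is 1:1 ("randomized in a 1:1 ratio to the treatment and control arms"). Control values are 3.00% fatal bleeding, 40.50% UDPB class 2 or higher, and 800 mL (SD 253); treated values are taken from each row. Subjects are ranked by fatal bleeding, then UDPB, then drainage (normal). The components are drawn independently, which is an assumption because the documents give no correlation. The test is Finkelstein-Schoenfeld with Z > 2.44 at the interim and Z > 2.00 on the full sample, 200,000 trials per cell. Figures are percentages.

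| Scenario | Table 3, N=39 | Sim. n=39 | Sim. n=40 | Table 3, N=56 | Sim. n=56 | Sim. n=57 |
|---|---|---|---|---|---|---|
| A = R (formal) | 91.3 | 91.3 | 92.1 | 99.5 | 99.5 | 99.6 |
| A worse, 40:60 | 88.1 | 89.3 | 90.1 | 99.3 | 99.3 | 99.4 |
| A worse, 50:50 | 87.1 | 88.7 | 89.6 | 99.2 | 99.2 | 99.3 |
| A worse, 60:40 | 86.0 | 88.2 | 89.0 | 99.2 | 99.1 | 99.2 |
| A better, 40:60 | 93.6 | 93.1 | 93.7 | 99.7 | 99.7 | 99.7 |
| A better, 50:50 | 94.2 | 93.4 | 94.1 | 99.7 | 99.7 | 99.8 |
| A better, 60:40, 456.6 mL | 94.7 | 94.5 | 95.1 | 99.8 | 99.8 | 99.8 |
| A better, 60:40, 465.6 mL | not given | 93.8 | 94.5 | not given | 99.8 | 99.8 |

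The formal row reproduces at both looks. The largest gap is in the worst row: 88.2 − 86.0 = 2.2 points.

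**5. Sensitivity to the variance.** Replacing the Finkelstein-Schoenfeld variance by a U-statistic variance for the log win ratio (8,000 trials per cell) gives 86.4% at n=39 and 87.2% at n=40 in the worst row, but 90.1% at n=39 in the formal row, where Table 3 has 91.3%. Neither version matches every row.

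**The case against.** The strongest reply is that the sentence in Section 11.6 never claims to hold across all scenarios. The plan names one formal scenario, its interim value is 91.3%, and that does exceed 88.1%. The sentence also refers to 40 per group, while the two lower rows are at 39. Under the named test at 40 per group, the simulation puts every scenario above 88.1%, with a minimum of about 89%. The simulation does not reproduce the 86.0% row closely, so it cannot show that 86.0% is the true floor. The size mismatch is one subject per group and errs on the conservative side, the 456.6 mL cell does not feed the formal estimate, and the stopping decision depends on the Z boundary, not on a predicted probability.

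All of that stands. It rules out a reading that someone comparing 88.1% with 86.0% might draw: that the plan overstates its stopping probability by 2.1 points (88.1 − 86.0). That difference holds only against the 39-per-group table and only if the sentence is a minimum over all rows. The reply still does not explain why an unlabelled bound was taken from one sensitivity row, why the table and text use different sizes, or why one mean breaks the pattern. No section reconciles these.

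**Conclusion.** The three discrepancies are real and can be checked on the page: an unlabelled interim figure that is neither the formal value nor the table minimum, a table run at 39/56 where the text plans 40/57, and one mean of 456.6 mL where the table's weighting gives 465.6 mL.

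Their effect is minor. In the Finkelstein-Schoenfeld simulation, moving from 39 to 40 per group adds about 0.6 to 0.8 points at the interim, and correcting the mean lowers its own row by about 0.7 points (94.5 to 93.8 at n=39). These sizes rest on independent components. The choice of variance matters more in the worst row: 89.0% against 87.2% at 40 per group.

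A reader might also infer that the final-power statement is wrong or that the trial is underpowered. Neither follows. The final figure agrees with Table 3's minimum of 99.2%, apart from a strict inequality that should read as at least, and the boundaries and the 120 randomized subjects are unaffected. This is a reconciliation point, not a design fault.

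**What to change.** - Rerun Table 3 at 40 and 57 per group with 465.6 mL in the last scenario. State which test variance was used and what correlation between components was assumed.
- In Section 11.6, report the interim stopping probability for the formal scenario, followed by the range across scenarios from that rerun, with both labelled. The present extremes of 86.0% and 94.7% should not be carried over: both come from 39-per-group rows, and the upper one from the row with the suspect mean.
- In Section 11.1 and the Synopsis, report final power for the formal scenario (currently 99.5%) and give the scenario minimum as at least that value (currently 99.2%), both updated from the rerun.
- Until the rerun is done, cite no interim floor other than 86.0% at 39 per group.

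The cost is one simulation run and edits to a few stated figures, with no change to the design.
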